4.4 Definitions

- *Bolus* – 10 - 20 ml/kg fluid (isotonic crystalloid, colloid, or blood product) up to 1 L and given within a 10 minutes period
- *Fluid responders* – Children who have a pre- and post-fluid challenge $\Delta VPeak > 10\%$ calculated using the equation ($\Delta VPeak_{pre} = (VPeakmax_{pre} - VPeakmin_{pre}) /$

Protocol #: 18-2513

PI: [name]

Version date: 07/01/2019

$$[(V_{peakmean_{pre}})] - (\Delta V_{Peak_{post}} = (V_{Peakmax_{post}} - V_{Peakmin_{post}}) / [(V_{peakmean_{post}})] \times 100$$

- *Multiple fluid challenges* – If more than one fluid bolus is administered at least 30 minutes apart, they will be reported as individual events
- *Pre-bolus measurements* – Hemodynamic measurements will be calculated or recorded three times thirty seconds apart and averaged just before a bolus is administered. Cine loops from IVC measurements will be recorded three times, thirty seconds apart for post-hoc CI calculation. Peak aortic velocity and CRI will be recorded on the EDM monitor and averaged over 90 seconds.
- *Post-bolus measurements* - Hemodynamic measurements will be calculated or recorded three times and averaged five minutes after a bolus is completed. These measurements will be time and repeated in an identical fashion to pre-bolus measurements.

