A plethora of indices and tools have been studied and marketed to assess intravascular volume status with only a few proven reliable with reproducible results. Based on pre-fluid challenge values, several of these tools have been used to predict who may benefit from additional fluid (fluid responders). Alternatively, some of these tools have been used to distinguish fluid responders from non-responders based on changes in pre- and post-fluid challenge values. Among these tools, the pulmonary artery catheter provides measurements of both left and right heart pressures which can be applied to calculate the cardiac output (CO) and stroke volume (SV). Changes in these values (e.g. an increase in the stroke volume by 10%) between pre- and post-fluid challenge have been used to define fluid responders. This devise, however, is invasive with several significant risks, and therefore is rarely used in children. Echocardiography, on the other hand, is a non-invasive bedside study also used to assess CO and SV but is expensive and requires trained echosonographers for application. Further, because a transthoracic probe is required to obtain the images, application in the operating room is difficult as the chest is often in the operating field limiting access to the echosonographer. Lastly, the esophageal aortic blood flow device (CardioQ-EDM, Deltex Medical, Chichester, UK) has been found in multiple adult and pediatric studies to reliably distinguish fluid responders from non-responders intensive care unit (ICU) and operating room [2-6]. Much like an orogastric tube, this device is simply placed by a provider in the patient's esophagus and uses Doppler waveforms to measure aortic blood flow velocities (**Figure 1**). Variations in the amplitude of peak velocities has been shown to corelate with intravascular volume status[2-6]. Specifically, a change in the peak velocity by greater than 10% between pre- and post-fluid challenge values has

Protocol #: 18-2513

[figure not shown]
PI: [name]

Version date: 07/01/2019

[figure not shown]
been shown to accurately distinguish those who are fluid responsive from those who are not with similar accuracy to echocardiography and pulmonary artery catheter readings[7].

Figure 1

A

B

Legend: A) Illustration of CardioQ-EDM position. In children age 15 years and younger, the device is introduced through the oral cavity. B) Correct placement confirmed by descending aortic waveform.

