ARTERIAL LINES	PPV, SVV, SPV
ESOPHAGEAL DOPPLER	ΔVpeak , SV, CO, ABF
CAPNOMETER	ΔETCO_2
NON-INVASIVE	
VITAL SIGNS	HR, SBP
PLETHYSMOGRAPHY	Plethysmography variation index
ULTRASONOGRAPHY	IVC CI
ECHOCARDIOGRAM	CO, SV
COMPENSATORY RESERVE INDEX	CRI

CO – cardiac output, SVR – systemic vascular resistance, SV – stroke volume, LV – left ventricular end-diastolic area index, GEDVI – global end-diastolic volume increase, CVP – central venous pressure, PCWP – pulmonary capillary wedge pressure, SvO_2 – mixed venous oxygen saturation, ΔpCO_2 – delta partial pressure of carbon dioxide, PPV – pulse pressure variation, SVV – stroke volume variation, SPV – systolic pressure variation, ΔVpeak – delta aortic blood flow peak velocity, ABF – aortic blood flow, ΔETCO_2 – delta end-tidal carbon dioxide level, HR – heart rate, SBP – systolic blood pressure, IVC – inferior vena cava, CI – collapsibility index, CO – cardiac, CRI – compensatory reserve index

While large series have evaluated the predictive utility of various devices in adults, reports appraising tools used to assess fluid responsiveness in children are limited with heterogeneous findings [16]. A systematic review by Gan et al. published in 2013 reviewed 12 pediatric studies that, in total, evaluated 24 markers of fluid responsiveness in 439 children. The only variable that was repeatedly found predictive of fluid responsiveness and distinguish fluid responders from non-responders was variation in aortic blood flow peak velocity (ΔVPeak) obtained from the CardioQ-EDM. Not only has this tool been shown to predict those who will benefit from additional fluid, but, based on changes in pre- and post- fluid ΔVPeak , in it has been shown to accurately distinguish fluid responders from non-responders [7].

[figure not shown]
In adults, the esophageal CardioQ-EDM has been used both in the operating room and ICU. Among adult trauma patients admitted to the ICU, CardioQ-EDM has been used to guide resuscitation and shown to decrease infection complications as well as reduce ICU and hospital length of stay [17]. In children, increased enthusiasm in recent years has led to a number of small clinical trials most of which have been performed in Europe. In a metanalysis published in 2016 included six studies and 163 ventilated children, comparing CardioQ-EDM to echocardiography the authors concluded that the area under the summary receiver operating characteristic curve to distinguish responders from

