non-responders for Δ VPeak was 0.94 [18]. While the optimal Δ VPeak varied from 7-20% among studies, one of the larger series using a Δ VPeak of 10% as a threshold found the sensitivity and specificity to be 100% in distinguishing fluid responders based on aortic velocity-time integrals identified by transthoracic echocardiogram [7]. Based on these results, we plan to define fluid responders as those who have $>10\%$ Δ VPeak between pre- and post-fluid challenge.

Bedside evaluation of the IVC to calculate the CI is a commonly used tool in adults [19, 20]. It serves as a surrogate to measure preload variation induced by mechanical ventilation. The technique requires limited ultrasonographic experience often at the critical care or anesthesia fellow level. In pediatrics, the predictive utility of IVC CI has only been evaluated in small series with conflicting results [21].

The CRI is another non-invasive devise using a photoplethysmographic probe (CipherOx-CRI) placed on the index finger. Based on data gathered from the probe, a computer-generated algorithm is then used to calculate a number between zero and one, referred to the CRI (Figure 3) [22]. The CRI correlates to one's intravascular volume status and proximity to hemodynamic collapse [23].

Figure 3

Legend: CRI, compensatory reserve index. CRI=1 is normovolemia and CRI=0 is the point at which the patient is at highest risk for hemodynamic decompensation.

Confounding factors that can influence dynamic measurements must also be considered. For instance, cardiac arrhythmias, small tidal volumes, spontaneous respiration, and high positive end-expiratory pressure have been found to decrease the predictive utility of pulse pressure variability and IVC CI [24-26]. Thus, it is paramount to use and apply these measurements in the appropriate clinical setting. Presumably, the influence confounding variables have on the predictive utility of these indices in children is similar to that of adults, however, comparative analyses have not been performed. Thus, when interpreted in the appropriate clinical context, these minimally and non-invasive devices are tools available to guide a balanced fluid resuscitation; however, while small series exist in various pediatric populations, validation is necessary in order to apply these tools in hypovolemic children with significant blood loss.

Protocol #: 18-2513

PI: [name]

Version date: 07/01/2019

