While numerous tools are available to guide resuscitation, one potential benefit of this project is to validate the use of CipherOx-CRI in this cohort. If CRI proves to be a valuable predictor of intravascular volume status and the need for volume expansion, this could negate the need for arterial line placement which is time consuming, invasive, and associated with complications such as arterial thrombosis. Furthermore, after validation in this cohort, additional studies could be performed in other groups of children at risk for hemorrhagic shock in the hopes to guide ongoing resuscitation accurately without the need for invasive devices.

3. Specific Aims and Hypotheses:

Aim I: Among infants undergoing cranial vault reconstruction for craniosynostosis, we aim to determine the proportion who respond to clinically administered fluid or blood products defined by pre- and post-fluid challenge $\Delta V_{Peak} > 10\%$.

Hypothesis Ia: We hypothesize that approximately half of the cohort will be fluid responsive defined by ΔV_{Peak} by $> 10\%$ after a 10 mL/kg fluid bolus is administered immediately following induction. Although this is a prediction, it is based on previous published reports suggesting a relatively even distribution among patients who clinicians believe need volume expansion. Additionally, because these children have a mean weight of 6.4 kg and will have been nil per os for several hours prior to surgery, they are at risk for intravascular volume depletion even prior to blood loss.

Hypothesis Ib: Because clinicians use pulse pressure variability, heart rate, systolic blood pressure, urine output, and blood loss to gauge need for ongoing resuscitation (either crystalloid, colloid, or blood), we suspect that more than half of subsequent fluid challenges will be given to infants who are fluid responsive (defined by a pre- and post-bolus ΔV_{Peak} of $> 10\%$).

Aim II: To determine the PPV, NPV, sensitivity, specificity, and optimal threshold for CRI, collapsibility index, pulse pressure variability, stroke volume variability, heart rate, systolic blood pressure, and mean arterial pressure as tools to predict fluid responsiveness using pre- and post-fluid challenge $\Delta V_{Peak} > 10\%$ to define fluid responders.

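### The responder rule is a fall in ΔVPeak of more than 10 percentage points, but the protocol's background attaches 10% to other quantities and does not justify a 10-point cut-off

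*Combined protocol and SAP*

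**What the plan says.** **The operative rule.** Section 4.4 (Definitions) describes responders as "Children who have a pre- and post-fluid challenge" ΔVPeak above 10%, and then gives the equation. This is the pre-bolus (max − min)/mean, minus the same ratio after the bolus, times 100. Section 4.6.5 defines ΔVpeak at one time point as (max − min)/mean × 100, which is already a percentage.

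**Where 10% appears in the background.**
- The text introducing the esophageal Doppler device gives a 10% rise in stroke volume as an example of a response criterion. It then gives "a change in the peak velocity by greater than 10% between pre- and post-fluid challenge values" as the Doppler criterion. The sentence just before that one reads "Variations in the amplitude of peak velocities has been shown to corelate with intravascular volume status".
- The review of pediatric studies after Table 2 says of pre-to-post changes in ΔVPeak that "it has been shown to accurately distinguish fluid responders from non-responders". It gives no cut-off.
- The rationale that follows reports optimal ΔVPeak values of 7–20% across studies. It says that one series using a ΔVPeak of 10% "as a threshold found the sensitivity and specificity to be 100% in distinguishing fluid responders based on aortic velocity-time integrals". It continues: "Based on these results, we plan to define fluid responders as those who have" more than 10% ΔVPeak between the pre- and post-challenge values.

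**Where the label is used.** Hypothesis Ia in Section 3 says "We hypothesize that approximately half of the cohort will be fluid responsive defined by" this rule. Aim II assesses the candidate indices "as tools to predict fluid responsiveness using pre- and post-fluid challenge" ΔVPeak above 10%. Section 4.8 compares responders with non-responders and screens confounders by their association with the same gold standard.

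**The concern.** One number, 10%, appears beside four quantities: a change in stroke volume, a change in peak velocity, a ΔVPeak threshold, and a pre-minus-post difference in ΔVPeak. These are not interchangeable. Peak velocity is a flow measure, whereas ΔVPeak is its respiratory variation. A cut-off that works for one does not carry over to another without evidence.

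The printed rule applies 10 to the last of these, and that is the only one for which the available text offers no supporting number. If the label departs from the criterion that the rationale relies on, the Aim I proportion is affected. So is every sensitivity, specificity, PPV, NPV and AUC in Aim II, because each is measured against that label, and so is the choice of confounders.

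**Working it through.** **Inputs.** The equation is from Section 4.4, the single-time-point definition from Section 4.6.5, and the cut-off of 10 from Section 4.4. The documents give no distribution of pre-bolus ΔVPeak, so all starting values below are illustrative assumptions. The 7–20% range in the background is a range of cut-offs, not of baselines, and is not used as one. The plan has no figure of its own to reproduce here.

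**Step 1: scale of the rule.** With ΔVPeak in percent, the equation gives pre − post. There is no division by the pre value, and no placement of the missing brackets would create one. If × 100 applied only to the post term, as the extracted text literally shows, the result could not exceed 2 (taking the mean as the midpoint of maximum and minimum) and no child could pass 10. That reading cannot be intended, and the bracketing may be an extraction artefact. The rule is therefore pre − post > 10 percentage points.

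**Step 2: who can never respond.** Since post ≥ 0, pre − post > 10 implies pre > 10. A bolus that starts at 10% or less cannot be a response, whatever its effect.

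**Step 3: size of fall required.** The required fall as a share of the start is 10/pre.

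| Pre-bolus ΔVPeak | Post-bolus must be below | Fall as share of start |
|---|---|---|
| 12% | 2% | more than 10/12 = 83.3% |
| 15% | 5% | more than 10/15 = 66.7% |
| 18% | 8% | more than 10/18 = 55.6% |
| 20% | 10% | more than 10/20 = 50.0% |
| 30% | 20% | more than 10/30 = 33.3% |

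**Step 4: comparison with the quantities in the background (assumed values).**
- *Change in peak velocity.* Mean velocity 100 to 115 is +15%. With ΔVPeak 15% to 9%, the fall is 6 points. This is a response on the velocity criterion and not on Section 4.4. Velocity 100 to 104 is +4%. With ΔVPeak 22% to 10%, the fall is 12 points, and the labels are reversed. Disagreement can run both ways.
- *Pre-bolus ΔVPeak above 10%.* By Step 2, every Section 4.4 responder meets this. The converse fails: 18% to 9% starts above 10% but falls only 9 points. The printed rule is a strict subset.

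**Step 5: Hypothesis Ia.** For about half the cohort to respond, about half must start above 10% and also fall by more than 10 points. If every bolus removed the same fraction f (an assumption), the median start would have to be about 10/f: 30% for f = 1/3, 20% for f = 1/2, 15% for f = 2/3. The documents give no data against which to check these values.

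**The case against.** The strongest reply is that the background may already supply the support. The three passages about ΔVPeak cite the same pediatric series. The introduction separates tools that predict from pre-bolus values from tools that distinguish responders by pre-to-post change, and the rationale uses the second verb for the 10% threshold before adopting a pre/post rule. On that usage, the series may have tested a 10% pre-to-post change. The peak-velocity sentence may also be loose wording for variation in peak velocity, since its preceding sentence is about variation.

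This stands as a limit on confidence but does not supply the justification. The verb does not settle the matter, because the reference-list titles of both the series and the meta-analysis in the same paragraph speak of predicting. Even if a pre/post change was tested, the available text does not say that it was a 10-point difference. What the series measured cannot be established here.

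A reader might also infer that the plan leaves the scale open between percentage points and a relative fall, since it writes % and Hypothesis Ia speaks of a change by more than 10%. The documents do not support that. Section 4.4 says the label is calculated from its equation, and the equation has no baseline denominator. The prose elsewhere is shorthand for the defined term. What remains on scale is a drafting fault: % is used where percentage points are meant.

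**Conclusion.** The concern holds as a gap in justification. The rule is a fall of more than 10 percentage points in ΔVPeak. In the available text 10% belongs to a change in stroke volume or peak velocity, or to a ΔVPeak threshold against echocardiography, and the one passage that supports a pre-to-post change in ΔVPeak has no number.

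The structural consequences are exact: no response is possible from a start of 10% or less, and the required fall is more than 83% of the start at 12%, 56% at 18% and 33% at 30%. The number of children mislabelled cannot be computed without a baseline distribution.

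Two further conclusions would go too far. The documents do not show that the 10-point cut-off is wrong, and they do not show that the cited series contradicts it. Confidence is moderate: the wording in the background may be loose, the series could not be consulted, and some introductory text was not available for this review.

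**What to change.** Before analysis:

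1. Print one correctly bracketed formula in Section 4.4 and state that it is in percentage points: 100 × [(max_pre − min_pre)/mean_pre − (max_post − min_post)/mean_post] > 10. Reconcile the background sentences, the aims and hypotheses in Section 3, and Aim I in Section 5 with it. Section 4.6.5 can stay as it is, since it defines the single-time-point component.
2. Justify the cut-off for this quantity. A single-time-point ΔVPeak threshold of 10% should not be cited as validation of a 10-point fall. If the cited series did test a pre-to-post difference, say so and give its scale.
3. Report how many boluses start at ΔVPeak of 10% or less, because these cannot be responses.
4. Pre-specify one sensitivity analysis that defines response as a change of more than 10% in mean peak velocity, 100 × (mean_post − mean_pre)/mean_pre, with its direction stated. Report agreement of the labels and the AUCs under both definitions.

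The cost is protocol wording and one extra analysis. Section 4.4 already has peak aortic velocity recorded before each bolus and repeated after it, so no new device, measurement or patient is needed. The downside is that the responder share may differ between definitions and both must then be reported.

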4.5 Decision for volume expansion

All children receive a 10 ml/kg crystalloid bolus immediately after induction. The need/decision for a fluid bolus will be determined by the anesthesiologist based on clinical judgement. Currently, the anesthesiologist places an arterial line at the beginning of the case and using pulse pressure variability, HR, SBP, MAP, urine output, and blood loss determines whether or not a fluid or blood bolus is appropriate. Data collected from the CardioQ-EDM, CipherOx-CRI, and bedside ultrasound will not be provided to the care team.

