Reporting bias will be minimized by limiting interactions between the study team and OR team. Furthermore, as all children receive a bolus prior to incision, independent of available indices used to assess intravascular volume status, bias should be minimized for this fluid bolus. As these devices are experimental in this patient population, anesthesiologists will be blinded to hemodynamic data generated by the CardioQ-EDM, bedside ultrasound, and CipherOx CRI. If data is needed in an emergent setting, the subject will be excluded from analysis. Although recorded measurements from the Cardio-Q EDM monitor will be visible to the study team, IVC measurements will be stored and calculated post-hoc by a co-investigator blinded to whether or not the subject is or is not fluid responsive. Additionally, a trained statistician not involved in data collection will be paid for analysis. It should also be noted at [name] is a paid officer of CipherOx but will not be involved in the data collection and analysis.

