4.8 Data Analysis

Protocol #: 18-2513

PI: [name]

Version date: 07/01/2019

Univariate comparisons between various measures will be compared between the fluid responder and non-responder groups using t-tests or Fisher's exact test for continuous and categorical measures, respectively. Area under the curve will be calculated for CI and CRI using both simple logistic regression models including no confounders and multiple logistic regression models including confounders. Confounders will be identified for inclusion in the multiple logistic regression models by calculating the univariate association with the gold standard (using a $p < 0.10$ threshold). These adjusted models will be used to verify thresholds for classification using CI and CRI which will then be applied to calculate classification summary measures (e.g., PPV, NPV, sensitivity, and specificity). Data analysis will be performed by a biostatistician funded by the Division of Pediatric Surgery using R and SAS statistical software programs.

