4.9.2 CardioQ-EDM Contraindications

- Doppler probes (DP240 and I2n) should not be placed in patients under 16 years of age. We will be using the KDP72 probe
- Do not use where nasal injuries are apparent or may have occurred.
- Do not use where nasal polyps exist.
- Do not use where there are circumstances of facial trauma.
- Do not use where there is a risk of brain injury.
- Do not use in patients undergoing intra-aortic balloon pumping.
- Do not use with carcinoma of the pharynx, larynx or esophagus.
- Do not use with aneurysms of the thoracic aorta.
- Do not use with tissue necrosis of the esophagus or nasal passage.
- Do not use in close proximity to laser surgery.
- Do not use in patients with pharyngo-oesophago-gastric pathology and/or severe bleeding diatheses.

5. Specific Aims:

Aim I: Define fluid responders based on aortic ΔV_{peak} : Among infants undergoing cranial vault reconstruction for craniosynostosis, we aim to determine the proportion who respond to clinically administered fluid or blood products defined by pre- and post-fluid challenge EDM $\Delta V_{Peak} >10\%$.

Mock-up Table 1: Demographics of Responders and Non-Responders to Initial 10 mL/kg bolus prior to surgical incision

Variable	Responders	Non-Responders	P-value
Demographics			
Age			
Weight			
Height			
BMI			
Gender			
Ethnicity			
Duration of NPO status			
Associated syndrome			

Legend: BMI, body mass index; npo, nil per os

Aim II: Calculate the PPV, NPV, sensitivity, specificity, and optimal threshold for CRI and collapsibility index as tools to prediction fluid responder

Protocol #: 18-2513

PI: [name]

[figure not shown]
Version date: 07/01/2019

		Fluid Responsive	
		Yes	No
CRI Threshold	+	True Positive	False Positive
	-	False Negative	True Negative

		Fluid Responsive	
		Yes	No
CI Threshold ($\geq 15\%$)	+	True Positive	False Positive
	-	False Negative	True Negative

Performance will also be calculated for heart rate, systolic blood pressure, mean arterial pressure, pulse pressure variability and stroke volume variability. Two separate analyses will be performed – one for the 10 ml/kg protocolized bolus provided immediately after induction and one accounting for all boluses provided.

Mock-up Figure

Mock-up Table 2 – Performance at predicting fluid responsiveness

Variable	Correlation (r)	AUC
IVC CI		
CRI		
SBP		
PPV		
SVV		
MAP		
HR		

Protocol #: 18-2513

PI: [name]

Version date: 07/01/2019

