Aim III: Evaluate confounding variables that may influence CRI or collapsibility index

Variable	Scale of Measurement	Data Point Location	Analysis Method
Outcome Variable IVC CI, CRI, PPV, SVV, HR, SBP, MAP AUROC	Interval	Pre-bolus measurements	
Confounding Variables Age Weight BMI Gender Ethnicity Associated syndrome Preoperative Hemoglobin Duration of NPO status Core temperature at time of bolus Paralysis provided (Y/N) Blood transfusion (Y/N) Total blood volume Total Crystalloid Total Colloid Vasopressor requirement Total amount of vasopressor Ventilation Tidal volume PEEP PIP Spontaneous breaths	Interval Interval Interval Dichotomous Ordinal Dichotomous Interval Interval Interval Dichotomous Dichotomous Interval Interval Interval Dichotomous Interval Interval Dichotomous	Demographics Demographics Demographics Demographics Demographics Demographics Demographics Preop results Anesthesia Rec Anesthesia Rec Ventilator Ventilator Ventilator Ventilator	Multivariable Linear Regression

Figure or Table will depend on results found. If neither of the outcome variables are affected by the confounding variables may only report this finding in the text.

Two separate analyses will be performed – one for the 10 ml/kg protocolized bolus provided immediately after induction and one accounting for all boluses provided.

Protocol #: 18-2513

PI: [name]

Version date: 07/01/2019

Reference:

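### The all-bolus analyses in Aims II and III name no method for repeat boluses within a child, and those two aims show clinically triggered boluses only pooled with the protocolised one

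*Combined protocol and SAP*

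**What the plan says.** Section 4.4 sets the unit of analysis: "If more than one fluid bolus is administered at least 30 minutes apart, they will be reported as individual events". Section 4.6 repeats the study measurements around each further bolus.

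Section 5 plans two analyses for Aim II and the same two for Aim III. One covers the protocolised post-induction bolus, the other is "one accounting for all boluses provided". That phrase says which boluses enter; it does not describe a within-child method.

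Methods are named in two places. Section 4.8 compares responders with non-responders by t-tests or Fisher's "exact test for continuous and categorical measures, respectively", and obtains AUCs from simple and multiple logistic regression. On covariate selection it says "Confounders will be identified for inclusion in the multiple logistic regression models by calculating the univariate association with the gold standard", at p < 0.10. The Aim III table names "Multivariable Linear Regression", and reporting there depends on the result: "If neither of the outcome variables are affected by the confounding variables may only report this finding in the text". No random effect, GEE, cluster-robust variance or cluster bootstrap appears in the text available.

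On later boluses, section 4.5 says the anesthesiologist, "using pulse pressure variability, HR, SBP, MAP, urine output, and blood loss determines whether or not a fluid or blood bolus is appropriate". CRI, IVC CI and esophageal Doppler data are withheld from the care team. Section 4.7 describes the pre-incision bolus differently: it is given "independent of available indices used to assess intravascular volume status, bias should be minimized for this fluid bolus".

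**The concern.** There are two separate problems.

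**Clustering.** Eight of the Aim III covariates cannot change between boluses in one child: age, weight, BMI, gender, ethnicity, syndrome, preoperative hemoglobin and fasting duration. A second or third bolus adds a row for these covariates but no new child. Ordinary regression counts the rows as independent, so if the index values within a child resemble each other, a child trait can be reported as affecting CRI or IVC CI when it does not. The p < 0.10 screen would have the same fault if run on all boluses, and would then pass too many child traits into the adjusted models.

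**Trigger selection.** Pulse pressure variability, heart rate, systolic pressure and mean pressure help decide whether a later bolus is given, and are then evaluated in Aim II alongside CRI and IVC CI, which had no part in that decision. Selecting on an index narrows its range among the selected boluses and lowers its AUC there. Pooling with unselected first boluses adds a contrast between bolus types that can push the other way. The stated goal is to replace arterial lines if a non-invasive index predicts as well or better, so a distorted comparison matters.

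**Working it through.** The text gives no sample size, ICC or expected number of boluses per child, so there is no plan figure to reproduce. All inputs below are assumptions: n = 30 children (section 4.2 lists 30 probes, single-patient per section 4.9.1; this is a supply count), m = 2 to 4 boluses per child including the first, ICC ρ = 0.1 to 0.7, and no true covariate effect.

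**1. Aim III regression.** I read the outcome as the pre-bolus index value. The table row also mentions AUROC, which has no per-bolus value. With total variance 1 and eight child-constant covariates plus an intercept:

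- between-child mean square B = 1 + (m − 1)ρ, the usual design effect; within-child W = 1 − ρ
- residual mean square s² = [21B + 30(m − 1)W] / (30m − 9), since 30 − 9 = 21 between-child degrees of freedom remain
- true size ≈ 2[1 − Φ(t / √(B/s²))], with t the 5% critical value

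Examples:

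- m = 2, ρ = 0.1: B = 1.1, s² = (23.1 + 27)/51 = 0.982, ratio 1.120, size about 5.8%.
- m = 4, ρ = 0.5: B = 2.5, s² = (52.5 + 45)/111 = 0.878, ratio 2.846, size about 24.0%.
- m = 4, ρ = 0.7: B = 3.1, s² = (65.1 + 27)/111 = 0.830, ratio 3.736, size about 30.5%.

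Simulation (4,000 runs per cell) agrees:

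| Boluses per child | ICC 0.1 | 0.3 | 0.5 | 0.7 |
|---|---|---|---|---|
| 2 | 6.2% | 9.4% | 12.5% | 15.9% |
| 3 | 7.4% | 12.9% | 19.0% | 24.7% |
| 4 | 8.6% | 17.0% | 24.5% | 31.3% |

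Expected false findings among eight covariates run from 8 × 0.062 = 0.5 to 8 × 0.313 = 2.5, against 8 × 0.05 = 0.4 nominal. The same regression on child means holds about 5%, and a random-intercept model 4-6%, so clustering is the cause.

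**2. The screen, only if run on all boluses.** Section 4.8 does not say which boluses it uses, or which test. Assuming t-tests, a nominal 10% screen passes 11-13% of null continuous covariates at ICC 0.1 and 14-29% at 0.3-0.7. With Fisher's test for binary covariates (prevalence 10-50%) the figures are 5-12% and 7-29%. At ICC 0.1 with two boluses, five t-tests and three Fisher tests select 0.7-0.8 covariates by chance, against 8 × 0.10 = 0.8 nominal: no excess.

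**3. Trigger selection.** Give a trigger index and a withheld index the same true AUC of 0.80 (separation √2 × Φ⁻¹(0.80) = 1.19 SD). Let first boluses be 50% responders, as in Hypothesis Ia. Trigger the top 30% or 50% of potential later boluses on the trigger index plus noise (SD 0, 1 or 2), with conditional correlation 0 or 0.3 between the indices. Among triggered boluses the trigger index's AUC falls to about 0.64-0.79 and the withheld index's to 0.75-0.80. After pooling with first boluses (1 to 3 triggered per first bolus):

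| Responders among potential later boluses | Pooled AUC, withheld minus trigger index |
|---|---|
| 50% | 0.00 to +0.05 |
| 65% | −0.05 to +0.02 |
| 80% | −0.09 to −0.01 |

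The true difference is zero throughout, so the sign of the bias cannot be known in advance.

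**The case against.** Much can be said for the plan.

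- Both aims already include an analysis of the protocolised bolus alone. It has one bolus per child, so each all-bolus result has a counterpart free of clustering. Mock-up Table 1 is also confined to that bolus. This stands and limits the harm.
- A reader might infer that the plan nowhere separates triggered boluses. It does: Hypothesis Ib concerns later challenges on their own. But it addresses only the proportion of responders and has no stated method or table, so the point is confined to Aims II and III.
- A reader might also infer that the authors overlooked which bolus is free of trigger selection. Section 4.7 shows that they recognised it. What is missing is any use of it in the Aim II and III analyses, whose relative roles are not stated.
- Clustering does not bias the AUC point estimate, and no effect on the CRI or IVC CI threshold has been quantified. The documents do not support a claim that clustering makes the Aim II AUCs wrong. Nor do they plan intervals for them, so poor interval coverage is not an error in the plan.
- The sizes rest on assumed numbers of children and boluses and an assumed ICC, on one reading of a damaged table, and on eight of the roughly twenty listed covariates. This stands. If few children have a second bolus, or the ICC is near 0.1, the inflation is small.

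None of this supplies a within-child method for the all-bolus analyses or a triggered-only result in Aims II and III.

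**Conclusion.** The point holds in limited form and should be fixed. The all-bolus Aim III regression, as written, has error rates above nominal whenever index values within a child correlate: about 6-9% for a 5% test at ICC 0.1, and 9-31% at 0.3-0.7, under the assumptions listed. The screen is affected only if it uses all boluses. Trigger selection is a separate fault in the pooled Aim II comparison. It would be tempting to conclude that pooling flatters CRI and IVC CI, because selection lowers the trigger indices' AUC among triggered boluses. The working does not support that: the pooled difference takes either sign, depending on how many potential later boluses are in responders.

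**What to change.** **1. Treat the child as the cluster in every all-bolus analysis.** For tests of association, including Aim III and the screen if it uses all boluses, use a random intercept for child or GEE with a small-sample-corrected variance. State which boluses the screen uses. For a rare binary child-level covariate use a child-level permutation test: at 10% prevalence, simulated corrected GEE ran at 2-15% for a nominal 10% test, with up to 11% of fits not converging.

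Compute AUCs, thresholds, sensitivity, specificity, PPV and NPV from the raw index or from fixed-effect (marginal) predictions only. Predictions must not include the child's random intercept. In simulation with a worthless index, fitted values that included it gave an average AUC of 0.82-0.95, against 0.53-0.56 from the fixed part alone; a threshold built that way could not be applied to a new child either. Any interval should come from a child-level bootstrap or, for AUCs and their differences, clustered DeLong.

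**2. In Aims II and III, report triggered boluses as their own stratum** beside the protocolised-bolus and pooled results. State in advance that the protocolised-bolus comparison is the one free of trigger selection and clustering, and that the triggered-bolus comparison is subject to trigger selection.

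**Cost.** Analysis-plan wording and a few lines of R or SAS, with no new data or procedures. Intervals will be wider and there is a little more analysis work. The protocolised-bolus comparison precedes surgical blood loss and is imprecise: with 30 children, 15 of them responders, a paired AUC difference has a 95% half-width of about 0.14-0.22 (assumed AUCs 0.8-0.9, marker correlation 0-0.3). It cannot alone answer the question about children with significant blood loss, so the later boluses should be kept and reported.
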